• To characterize the risk preferences of compliers, we will run the first stage regression (6.2) separately for individuals with $R_i > 0$, $R_i = 0$ and $R_i < 0$ and compute the relative likelihood that a complier is risk averse/risk neutral/risk loving, which is given by the ratio of the estimated response to the lottery in the respective group to the response in the full sample. A higher relative likelihood for the $R_i < 0$ group supports our hypothesis that a complier is more likely to be someone with a preference for risk. We will follow the same procedure for groups formed from different combinations of α_i and r_i in order to test, for example, whether a complier is more likely to have convex utility and overweight small probabilities.

[H6d] Individuals who are impatient and who display a present bias respond more to the lottery offer. Thus, the intervention has a larger effect on individuals who engage most in risky lifestyles that offer immediate reward and invest least in preventive health behavior that gives a long-run gain for a short-run cost.

Elaboration

Benefits from preventive care and health behaviour are derived in the long run. Individuals who discount the future more are expected to invest less in prevention and indulge more in lifestyles that yield immediate benefits but carry long-term health risks. Conversely, those who discount less aggressively are more likely to be always takers of preventive care and healthy behaviours.

The chance to win a lottery brings the benefits from preventive care forward, which is valued most by the least patient individuals. Hence, these subjects are more likely to respond to the lottery offer.

Investment in preventive care can be further discouraged by present bias – the tendency to place additional weight on costs and benefits experienced immediately resulting in a discount rate over a length of time that is higher when the period begin in the present. Such bias can result in failure to implement plans for healthier living. From a distance, diet or exercise in the future can seem desirable but when the time comes to start dieting or exercising the immediate costs outweigh the heavily discounted long-term gains.

The opportunity to enter a lottery conditional on going for a checkup at a RHU/CHC gives the respondent the chance of a more immediate reward for the cost of taking this preventive action. Hence, it may help counter present bias.

Test:

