• We will characterize respondents according to their degree of impatience and whether they display present bias by implementing an instrument used by Ashraf et al (2005) to examine how these traits influence the response to the offer of a savings product in the Philippines. This involves a standard procedure of asking respondents hypothetical questions about whether they would choose to receive a smaller amount of money now or a larger amount in one month. By varying the amount of money offered in one month, respondents who discount more aggressively can be distinguished.

- To identify present bias, respondents are asked to choose between receiving a smaller amount in six months or a larger amount in seven months. Those who choose the smaller amount now rather than the larger amount in one month but who are prepared to wait seven months for the larger amount rather than accept the smaller amount in six months display present bias, or hyperbolic discounting. Those who choose the larger amount in one month rather than the smaller amount now, but who choose the smaller amount in six months rather than the smaller amount now, but who choose the smaller amount in six months rather than the larger amount in seven months also display time inconsistency. We will examine whether response to the lottery differs in this group but since noise is likely to be largely responsible for this type of inconsistency, we do not expect systematic variation in the response of this group relative to others.
- Using these stated choices, we will form groups of respondents who are more/less impatient and who do or do not display present bias.
- In the first stage regression, analogous to the procedure described in [H6c], we will interact the lottery instrument with indicators of the degree of impatience and with an indicator of whether the respondent displays present bias.
- We will then compute and compare the relative likelihoods that a complier is present-biased and impatient to varying degrees.

[H6e] Individuals who underweight small probabilities experience a higher reduction in risk factor exposure and increase in medication through PhilPEN than individuals who weight probabilities linearly and individuals who overweight small probabilities.

Elaboration

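### H6d: with impatience graded on the now-versus-one-month choices, the present-bias interaction measures present bias relative to consistent impatience, so it can be zero, negative or understated when both traits raise the lottery response

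*Combined protocol and SAP*

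**What the plan says.** The hypothesis names two traits: "Individuals who are impatient and who display a present bias respond more to the lottery offer". The test first describes a near frame, asking respondents "whether they would choose to receive a smaller amount of money now or a larger amount in one month", and says how this grades impatience: "By varying the amount of money offered in one month, respondents who discount more aggressively can be distinguished".

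The far frame, six versus seven months, is introduced to identify present bias. The present-biased are "Those who choose the smaller amount now rather than the larger amount in one month but who are prepared to wait seven months" to receive more. The opposite pattern (patient now, impatient later) is recognised as a separate inconsistent group that is expected to be mostly noise.

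The groups are then formed: "Using these stated choices, we will form groups of respondents who are more/less impatient and who do or do not display present bias". The lottery interactions, modelled on those of [H6c], are described next: "we will interact the lottery instrument with indicators of the degree of impatience and with an indicator of whether the respondent displays present bias". No equation is written for H6d, but equation (6.4) under [H6c] enters two trait interactions in one regression.

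A second analysis follows: "We will then compute and compare the relative likelihoods that a complier is present-biased and impatient to varying degrees". Under [H6c] this is a quantity "which is given by the ratio of the estimated response to the lottery in the respective group to the response in the full sample".

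**The concern.** The elaboration of H6d treats impatience and present bias as distinct reasons for under-investing in prevention, and expects each to strengthen the response. The coding does not keep them distinct. The present-bias indicator can equal one only where near-frame impatience also equals one, so no present-biased respondent can fall in the most patient near-frame grade.

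Once the impatience interaction is in the model, the present-bias interaction has no patient respondents to be compared with. It is a contrast with people who are impatient in both frames. The plan does not say this, and a reader would take a null or negative coefficient as evidence against the present-bias half of H6d. The lottery estimate is a complier effect, so a wrong account of who the compliers are would also affect how that estimate is described.

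**Working it through.** **Inputs.** The definitions come from [H6d]. The documents give no figure for H6d to reproduce, and no effect sizes, type shares or amounts. These are assumed:
- c is the lottery response (difference in attendance, lottery versus control) in patient respondents, set at 0.50.
- a is the extra response of the consistently impatient, 0 to 0.10.
- b is the extra response of the present-biased, 0 to 0.20.
- r is the extra response of reverse-inconsistent respondents, 0 or 0.10.

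**Coding at one pair of amounts** (I = near-frame impatient, PB = present-biased).

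| Group | Near | Far | I | PB | Lottery response |
|---|---|---|---|---|---|
| Patient in both | wait | wait | 0 | 0 | c |
| Impatient in both | now | earlier | 1 | 0 | c + a |
| Present-biased | now | wait | 1 | 1 | c + b |
| Reverse-inconsistent | wait | earlier | 0 | 0 | c + r |

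**Joint model.** Response = k0 + k1·I + k2·PB. Leaving the reverse group aside, k0 = c, k0 + k1 = c + a and k0 + k1 + k2 = c + b. Hence k1 = a and k2 = b - a, whatever the group shares.

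| a | b | k2 (present-bias coefficient) |
|---|---|---|
| 0.10 | 0.10 | 0.00 |
| 0.10 | 0.05 | -0.05 |
| 0.10 | 0.20 | +0.10 |
| 0.05 | 0.15 | +0.10 |
| 0.10 | 0 | -0.10 |
| 0 | 0.10 | +0.10 |

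**Reverse group included** (assumed shares: 38% patient, 25% present-biased, 25% impatient in both, 12% reverse). k2 is still b - a, because both groups in that contrast have I = 1. The reference now pools patient and reverse respondents. With a = b = r = 0.10, k0 = 0.50 + 0.10 × 12/50 = 0.524 and k1 = 0.60 - 0.524 = 0.076. The sum k1 + k2 is then 0.076 instead of b = 0.10.

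**Several amounts.** A population of 400,000 was simulated, 40% of them with a present-bias factor, answering the same amounts in both frames. Impatience was entered as near-frame grade indicators, with a = 0.10.

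| Amounts | b = 0.05 | b = 0.10 | b = 0.20 |
|---|---|---|---|
| 1 | -0.05 | 0.00 | 0.10 |
| 2 | -0.011 | 0.039 | 0.139 |
| 3 | 0.004 | 0.054 | 0.154 |

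No present-biased respondent was in the most patient grade. With three amounts they spread over the other grades (7.6%, 27.6% and 64.8%). Grading on the far frame returned b in every case.

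**Analyses that do not condition on the other trait** (shares 45% patient, 25% present-biased, 30% impatient in both).
- With a = b = 0.10, the full-sample response is 0.45 × 0.50 + 0.55 × 0.60 = 0.555, so the present-bias complier ratio is 0.60/0.555 = 1.08. A present-bias interaction entered alone is 0.10 - 0.10 × 30/75 = 0.06.
- With a = 0 and b = 0.10, near-frame impatience entered alone shows 0.10 × 25/55 = 0.045, although impatience has no effect.

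**Four groups.** With separate indicators for the last three rows of the coding table, the coefficients are a, b and r.

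**Far frame alone.** The impatient group then pools impatient-in-both with reverse respondents. If the latter respond like patient people, a = 0.10 is estimated as 0.10 × 25/37 = 0.068. The present-bias coefficient stays at b.

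**The case against.** A reader might infer that the present-bias interaction must vanish whenever H6d is true for both traits. The documents do not support that. The coefficient is b - a, which is zero only when the two effects are equal and the grade is binary. The sentence on varying the amount, and the later references to degrees of impatience, point to several grades. The overlap then attenuates the coefficient rather than cancelling it, and the present-biased are not all in one impatience category.

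Three further points deserve weight.
- The group-formation sentence comes after both frames have been described and could cover a cross-classification. The reverse-inconsistent group is already singled out, and the amounts would be in the baseline instrument (Appendix C), which is not in the text reviewed. This stands as far as it goes: the coding is partly open. But near-frame grading is the only grading described, so the text needs to say if another is meant.
- No information is lost. With a binary grade, the contrast of present-biased with patient respondents is the sum of the two interactions. This is true if reverse-inconsistent respondents have their own indicator, but the plan does not name that sum as the test.
- The complier ratios are not cancelled by the overlap. This is also true. They describe each trait marginally, so they cannot separate the two effects.

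**Conclusion.** The point holds in a limited form. On the grading described, and with both interactions in one regression, the present-bias coefficient does not estimate the effect H6d claims. It estimates present bias minus impatience with a binary grade, and an attenuated version with graded amounts. It may be zero, negative or understated when H6d is true for both traits. The b - a result follows from the definitions and does not depend on group shares. The graded results depend on the assumed population.

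Power figures are illustrative only. With 1,361 per arm, 10% control attendance, a 45-point lottery response in patient respondents, shares of 45% patient, 30% impatient in both, 15% present-biased and 10% reverse, and both traits adding 15 points, the joint coding detected present bias in 5% of 600 simulated trials and four groups in 88%. Those shares and effects are assumed, and the clustering by barangay was ignored although the plan assumes an ICC of 0.1.

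H6d is a secondary hypothesis about who complies. The principal outcome, the main instrumental-variable estimate and the sample size are untouched, so this is a minor correction.

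**What to change.** Write the H6d regression out. At the same pair of amounts in both frames, form four exclusive groups: patient in both (reference), impatient in both, present-biased, and reverse-inconsistent. Include the group main effects and interact the lottery indicator with the last three. Test present bias as present-biased versus reference, and impatience as impatient-in-both versus reference. Also report the complier ratios for these four groups.

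If near-frame impatience indicators are kept with a binary grade, state that present bias is tested by the sum of the impatience and present-bias interactions, and add the reverse-inconsistent indicator with its own interaction. Grading impatience from the far frame alone is not an equivalent substitute unless the reverse-inconsistent group is entered separately. The text also mentions varied amounts only for the one-month choice, so far-frame grading by degree may not be possible.

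The cost of the four-group version is wording in the analysis plan, since both frames are already asked. The sponsor should confirm from the questionnaire that at least one pair of amounts is common to both frames.

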5.1 Common issues

Two interventions will be allocated to respondents – the provision of information on CVD risk and the offer of a lottery ticket conditional on going for a checkup. The study is a randomized parallel experiment with two separate, non-overlapping treatment groups and one control group. Randomization will be done at the level of the barangay, which is the smallest administrative unit in the Philippines roughly equivalent to an electoral ward.

Soliciting the participation of the LGUs. After the sample barangays have been drawn and assigned to the treatment arms, the study team will schedule visits with the corresponding local chief executives (LCE) and the municipal/city health officer (MHO/CHO) to solicit their participation. A standard letter will be delivered stating the aims of the study and clarifying that several barangays in a municipality will be assigned to different treatment arms. An agreement will be drafted stating the responsibilities of UPecon Foundation R4D Study Team and the Local Government Units (LGUs). The terms of the agreement will explicitly state which barangays will be included in the study and in which barangays sampled residents will be given the lottery tickets on condition of attendance at the RHU/CHC. We will explore whether the budget will allow giving a small token of appreciation to the LCE and the MHO after the follow-up survey is completed, signalling the end of the field work part of the study.

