10.2 Results

Required sample sizes under the main scenario for parameter values described in the previous sub-section are given in Table 6. Estimates under alternative scenarios are given in Appendix B Tables B1-B4. The requisite sample size differs little across the outcomes but is slightly larger for the binary outcomes. We will set the sample size to that required to have sufficient power to test for the specified minimal effect size on the binary outcomes under the main scenario.

Table 6: Sample size calculations – Main scenario (1)

	Mean CVD risk	Mean systolic BP in mm Hg	Mean BMI	Mean waist circumference in cm	Binary outcomes
Required sample sizes					
Info treatment per round (unadjusted)	287	293	287	293	299
Lottery treatment per round (unadjusted)	1,306	1,333	1,306	1,333	1,361
Control per round (unadjusted)	1,306	1,333	1,306	1,333	1,361
Total baseline sample (adjusted)	4,816	4,916	4,816	4,916	5,019
Total follow-up sample	2,899	2,959	2,899	2,959	3,021
Number of clusters	290	296	290	296	303
Avg. cluster size at baseline	16.61	16.61	16.61	16.61	16.56

In implementing the sampling design, we will sample 303 barangays out of 849 distributed across the 32 municipalities and cities in Nueva Ecija province. We will meet with the mayors of all 32 municipalities to introduce the study, get their consent and endorsement of our field activities within their jurisdiction. This will be done during the field mobilization phase (see Table 2).

Since treatment will be randomized at the barangay level, there is no issue of contamination across households within a barangay. But since one RHU/CHC typically serves more than one barangay (there are 63 RHU/CHCs in the province), contamination through the same facility serving both treatment and control barangays needs to be considered. This is not an issue for the information intervention and control groups since the former does not require that the RHU/CHC do anything. The facility will be unaware of patients that belong to these two groups. There could be an issue if the role of the RHU/CHC in implementation of the lottery causes it to operate differently for all patients. One possibility is that it

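### Local governments are asked to agree after barangays are assigned and the lottery barangays named, and the plan has no rule for a refusal

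*Combined protocol and SAP*

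**What the plan says.** Section 5.1 sets the order of events: "After the sample barangays have been drawn and assigned to the treatment arms, the study team will schedule visits" with the local chief executive and the municipal or city health officer, to ask them to take part. The letter they receive is described as "clarifying that several barangays in a municipality will be assigned to different treatment arms". The agreement names every study barangay. It also identifies those of the lottery arm, that is, "in which barangays sampled residents will be given the lottery tickets on condition of attendance at the RHU/CHC".

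Section 10.2 gives the scale, "we will sample 303 barangays out of 849 distributed across the 32 municipalities and cities", and the level of consent: "We will meet with the mayors of all 32 municipalities to introduce the study, get their consent and endorsement". Table 2 puts field mobilisation in May to July 2017 and the baseline survey in August and September.

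Section 12 describes the mayor's letter. It covers the survey and interventions and, as a further request, seeks permission to involve the local health unit in the lottery.

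On contamination through shared facilities, Section 10.2 says "This is not an issue for the information intervention and control groups", and adds "The facility will be unaware of patients that belong to these two groups". Under Section 5.3 the facility is sent the names and addresses of voucher recipients only.

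The documents give no rule for a municipality that declines, in whole or in part, or for replacing its barangays. The 15% refusal allowance in Section 10.1 concerns individuals.

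**The concern.** In a cluster trial, those who control access to the clusters should commit before they know the allocation. Otherwise the decision to take part can depend on the arm. Here the mayor and health officer see how many lottery barangays they have drawn, and where, before they sign. Only the lottery gives the health unit extra work (checking vouchers, assessing claimants, issuing tickets, keeping records), so the allocation they see also shows the workload they would accept.

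Two kinds of loss could follow. A municipality might accept the survey and decline the lottery, which removes lottery clusters selectively. Or it might decline altogether, perhaps more readily where it drew many lottery barangays. Separately, an official holding the full list with the lottery barangays marked knows which other barangays are under study.

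**Working it through.** **Inputs.** Follow-up sample in Table 6, binary-outcome column: 1,361 lottery, 1,361 control, 299 information; about 10 people per cluster; 32 municipalities and cities (Section 10.2). ICC 0.1, baseline correlation 0.6, compliance 0.6, effect 0.2 SD (Section 10.1). A two-sided 5% test is assumed, since the sides are not stated.

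**Reproducing the plan.** 1,361 + 1,361 + 299 = 3,021, and 3,021/10 = 302.1, rounded up to 303 clusters, as stated. For mean CVD risk, 382.3 per arm × design effect 1.9 × (1 − 0.36) = 464.8. That rounds up to 47 clusters, or 470 people, and 470/0.36 = 1,305.6, against the stated 1,306. The sample sizes are not in dispute.

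**Clusters by arm.**

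- Lottery: 303 × 1,361/3,021 = 136.5
- Control: 136.5
- Information: 303 × 299/3,021 = 30.0

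**Clusters per municipality.** 303/32 = 9.5 on average: 4.3 lottery, 4.3 control and 0.9 information. If the 303 were spread evenly (an assumption; municipalities surely differ in size), the lottery count would have SD √(9.47 × 0.45 × 0.55) = 1.5. Lottery minus control would have SD √(9.47 × 0.90) = 2.9. Stratification is by urban/rural status (Section 10), not by municipality, so nothing holds these counts equal.

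**What the list reveals.** Marking the lottery barangays discloses the arm of 136.5/303 = 45% of clusters. A listed barangay not marked as lottery is a control with probability 136.5/(136.5 + 30.0) = 82%, and information otherwise.

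**Whole-municipality refusal.** The effect on power is small if arms are lost in proportion. Power = Φ(0.2 × 0.6/√(1.9 × 0.64 × 2/n) − 1.96), with n = 1,361 × (1 − k/32):

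| Municipalities refusing (assumed) | 0 | 1 | 2 | 3 | 4 | 5 |
|---|---|---|---|---|---|---|
| Power, lottery vs control | 81.0% | 79.8% | 78.5% | 77.1% | 75.7% | 74.1% |

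**Lottery-only refusal.** Suppose k municipalities decline the lottery but keep their control clusters. The control arm then contains a share f = k/32 of people from those municipalities, and the lottery arm contains none. If untreated outcomes there differ from elsewhere by D, the arm contrast shifts by f × D. D is unknown. Taking D = 0.2 SD purely as a yardstick, the shift is 0.2/32 = 0.006 SD for one municipality and 0.2 × 5/32 = 0.031 SD for five. The contrast that the trial is powered to see is 0.2 × 0.6 = 0.12 SD. The shift scales with D and ignores baseline adjustment, which would absorb part of it. This illustrates the mechanism and is not an estimate.

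**The case against.** Much of the opposing case is sound. Agreement is given by municipality, each municipality generally holds several arms, and no barangay-level consent is described. Households are chosen by interval sampling (Section 8), not by officials. A complete refusal therefore generally costs clusters in every arm, and within the municipalities that remain, which barangay holds which arm is still random. Refusal may also be rare: Section 12 promises no added cost to local government. Some disclosure cannot be avoided, because facilities issue the tickets and receive voucher holders' addresses.

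A reader might infer two stronger points, and the documents support neither.

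- **That Section 10.2 is contradicted.** It says that facilities will not know which patients are in the information and control groups. Nothing in Section 5.1 gives them those names or separates information from control barangays. An address could show that a patient lives in a listed barangay, but not that the patient was sampled.
- **That late agreement breaks the randomisation.** With whole-municipality refusal it puts mainly between-municipality balance at risk. Arm-selective loss needs a partial refusal.

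Section 10.2 also admits that facilities might change how they treat patients, says that they will be encouraged to operate as before, and argues that identification survives. It discusses this as a result of the facility's lottery role, not of a barangay list.

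The objection does not remove the partial refusal. The documents neither describe nor exclude it, and the separate lottery permission in Section 12 makes it a natural outcome.

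**Conclusion.** The point holds as a weakness in the order of recruitment. Participation, or lottery participation alone, can be decided with allocation known, and the plan does not say what happens then. A lottery-only refusal is the more serious case because it takes clusters from one arm: about 4.3 of 136.5 lottery clusters per municipality on average. A complete refusal removes about 9.5 of 303 clusters, mostly across arms, and costs about one percentage point of power for the first municipality lost.

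The per-municipality figures are averages. Without a refusal rate, or any information on how refusing municipalities would differ, the size of any bias cannot be stated. No figure in the sample size tables changes. The assurance in Section 10.2 stands for patients, with the qualification that non-lottery study barangays can be identified by subtraction.

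**What to change.** 1. Obtain signed agreement covering both the survey and the lottery from the 32 municipalities before the allocation is drawn, or while it is sealed. Randomise only barangays in municipalities that agree.
2. Let the agreement describe the arms without listing barangays by arm. After allocation, tell each RHU/CHC only what it needs to issue tickets: its lottery barangays and the voucher-holder lists. This does not hide the lottery barangays from facilities, which is not achievable, but it does keep the non-lottery study barangays off the list.
3. State in advance how a later refusal or withdrawal is handled and reported, including refusal of the lottery alone.
4. If the named list is kept, qualify Section 10.2 to say that patients cannot be identified but non-lottery study barangays can.

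The cost is a re-ordering of visits already planned for field mobilisation and edits to the letter and agreement. There are two downsides. Local governments commit without knowing which of their barangays will have the lottery. And if any municipality refuses, the sampling frame narrows from all 849 barangays to those in agreeing municipalities, which should be reported.
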